NCT 04883060

Midline Measuring Device Protocol

PI: [name] III Protocol Date: 7-10-2017

Midline Measuring Device Protocol

PI: [name] III

Methods:

The Wishbone was then used to assist in the posterior burr hole localization procedure for patients undergoing VPS

The Wishbone secures to the patient's skull by way of 2 adjustable caliper arms that are reversibly placed into the left and right external auditory canals. Smooth spheres at the terminal ends of the caliper arms make firm, secure contact with the skull in this manner. Each caliper arm has a hinge-like attachment to a midline sighting housing to which a laser pointer is mounted. Symmetric sliding caliper alignment arms extend from the midline housing and connect to each caliper arm. The sliding caliper alignment arms ensure that the left and right caliper arms move symmetrically relative to the midline and maintain a congruent angular offset between the left and right caliper arms and the midline housing. The laser pointer attached to the midline housing dock is oriented such that the laser beam always bisects the angle between the 2 caliper arms and thus is equidistant from the 2 external auditory canal spheres. When the Wishbone caliper arms are attached to the patient's left and right external auditory canals, the laser beam always illuminates a midline scalp point, even when the patient's hair is present.

Protocol:

1. Placement of the Wishbone

The Wishbone is designed specifically for use during posterior VPS surgery. After the induction of general anesthesia, the patient is positioned supine and sufficient hair is clipped to expose the right posterior scalp and midline. While the patient's head is positioned flat on the bed, the Wishbone caliper arms are adjusted, and the 2 external auditory canal spheres are firmly positioned within the left and right external auditory canals. Once the adjustment knob is tightened, the caliper arms are locked in position and the device is secured to the patient's skull. Initially, the device is rotated so that the laser beam is directed at the forehead just above the nose. If the laser beam illuminates the skin in the midline immediately above the nose, this indicates that the Wishbone has been appropriately secured to the skull. Next, an assistant flexes the patient's head and neck so that the surgeon can visualize the patient's posterior scalp. The device is rotated posteriorly so that the laser pointer illuminates the posterior midline. The surgeon uses a scalp marker to trace the posterior midline as delineated by the laser. The assistant should hold the device still to ensure that the device does not slip out of the ears, especially in patients with a larger ear canal, while the surgeon is rotating the device posteriorly with the laser turned on and ensuring that the laser is moving in a straight line from the anterior to the posterior midline. This calibration process is demonstrated in the mandatory training session. A second line is manually traced parallel to the midline and 3 cm offset to the right. This second line delineates how far off of the midline the burr hole will be located. Different techniques can be used to plan the rostrocaudal location of the burr hole. One method involves measuring up from the external occipital protuberance (typically, 7 cm). Another involves using frontal scalp and external ear landmarks to

project a line posteriorly to determine the optimal posterior scalp rostro-caudal location. The burr hole location is determined by the intersection of the 3 cm paramedian line and rostrocaudal measurement. In anticipation that pen marks on the scalp may be washed away or poorly visualized following the initial prepping and draping, surgical staples are placed on the designated burr hole location and adjacent midline to insure visibility of these landmarks during the surgical procedure

2. Measurements

We recorded the time from initial placement of the Wishbone until the midline scalp was marked in patients undergoing VPS surgery. The location of the Wishbone-localized midline staple was identified on each patient's postoperative computed tomography (CT) scan, and the true anatomical midline was defined by drawing a line joining the most anterior with the most posterior point on the falk attachment at the level of the axial CT cut of interest on the reconstructed sequence. This method for defining the anatomical midline was used as it has been shown previously to have the highest interobserver agreement rate. The distance from the Wishbone-determined midline scalp staple to the anatomical midline was defined as "distance from anatomical midline." The distance from the staple to the lateral edge of the sagittal sinus was defined as "distance from sinus." Finally, we measured the distance from the estimated center of the burr hole to the anatomical midline to generate a separate and complementary set of measurement data to study the Wishbone's localization accuracy. The distance was reported in positive values if the staple was to the patient's right of midline and negative values if it was to the left. The staples were removed on postoperative day 1 following the CT scan during the routine dressing change before discharge. If the staple was to the left of midline on the postoperative imaging studies, the distance measurement was assigned negative values.

Statistical Plan:

Statistical Analysis Data analysis was performed in R (3.5.1; R Foundation for Statistical Computing, Vienna, Austria) and GraphPad Prism 7 (GraphPad Software, San Diego, California, USA). Shapiro test was performed to test for normality. Mean, median, standard deviation (SD), and 95% confidence interval (CI) values were calculated and reported. Wilcoxon signed-rank test (nonparametric) was used to detect statistical difference with theoretical medians. $P < 0.05$ (2 tailed) was considered statistically significant

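### Accuracy is summarised from signed staple distances, in which left and right errors cancel; no absolute-error summary or tolerance is planned

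*Combined protocol and SAP*

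**What the plan says.** The Measurements section defines the distance from the Wishbone-placed midline staple to the anatomical midline on the postoperative CT. Right is positive and left is negative, a convention given twice, the second time as "If the staple was to the left of midline on the postoperative imaging studies, the distance measurement was assigned negative values".

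Two further distances are measured. One runs from the staple to the sagittal sinus ("The distance from the staple to the lateral edge of the sagittal sinus was defined as" the distance from sinus). The other runs from the burr-hole centre to the midline and is described as "a separate and complementary set of measurement data to study the Wishbone's localization accuracy". The burr hole has a planned position, set in the Placement section: "A second line is manually traced parallel to the midline and 3 cm offset to the right". That is a target, not a tolerance.

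The Statistical Plan has three elements for these data:

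- A check of distribution, by the Shapiro test.
- Summary statistics, listed without saying which parameter the interval is for: "Mean, median, standard deviation (SD), and 95% confidence interval (CI) values were calculated and reported".
- One hypothesis test on the distances, which is a test of location: "Wilcoxon signed-rank test (nonparametric) was used to detect statistical difference with theoretical medians".

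Significance is two-tailed at 0.05. The reference medians are not stated; 0 for the staple is the natural reading. The document contains no absolute distance, proportion within a limit, tolerance or success criterion.

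**The concern.** The burr-hole line is drawn from the midline mark, so the accuracy question is how far off that mark may be in a given patient, in either direction. A signed mean or median does not answer it: a staple 8 mm left and one 8 mm right average to zero. The signed-rank test has the same limitation, since against any fixed reference it assesses location, not size of error.

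The SD does show scatter, and with the mean it gives the root-mean-square error (RMSE) without assuming a distribution. It does not give the upper tail, or the share of patients beyond a limit, unless a distribution is assumed.

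The plan does not say that a non-significant Wilcoxon result will be read as accuracy. It is, however, the only test applied to the distances, and no other criterion is given. At a fixed bias, a more scattered device is less likely to be flagged, so a non-significant result is not evidence of accuracy.

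**Working it through.** The plan gives no sample size, SD, bias or limit, so it has no figure to reproduce. All numerical inputs below are assumptions. The sign convention, the list of statistics and the 0.05 two-tailed level come from the Measurements section and the Statistical Plan.

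**1. Two sets with the same planned distance summaries.** Take n = 20 and SD = 5 mm, so the sum of squares about a mean of 0 is 25 × 19 = 475.

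- Set A: nine staples at +2 mm, nine at −2 mm, one at +x and one at −x. Then 18 × 4 + 2x² = 475, so x = √(403/2) = 14.2 mm.
- Set B: ten at +y and ten at −y. Then 20y² = 475, so y = 4.87 mm.

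The CI half-width is t(19) × SD/√n = 2.093 × 5/√20 = 2.34 mm. RMSE = √(mean² + SD² × 19/20) = √23.75 = 4.87 mm.

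| | Set A | Set B |
|---|---|---|
| Mean, median (mm) | 0, 0 | 0, 0 |
| SD (mm) | 5.0 | 5.0 |
| 95% CI for mean (mm) | ±2.34 | ±2.34 |
| Wilcoxon p against 0 | 1.0 | 1.0 |
| RMSE (mm) | 4.87 | 4.87 |
| Shapiro p | 0.0001 | 0.000008 |
| Mean absolute error (mm) | 3.22 | 4.87 |
| Median absolute error (mm) | 2.0 | 4.87 |
| Maximum absolute error (mm) | 14.2 | 4.87 |
| Beyond 4 mm | 10% | 100% |
| Beyond 10 mm | 10% | 0% |

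B looks worse at a 4 mm limit and A looks worse at 10 mm. The planned summaries of distance cannot separate them. Shapiro rejects normality in both, which warns against a normal approximation but does not say which set has the larger errors. That approximation would give 2Φ(−4/5) = 42% beyond 4 mm for both sets.

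**2. What the Wilcoxon test responds to.** Simulated one-sample test against 0, normal errors, 10,000 runs per cell. RMSE = √(bias² + SD²).

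| Bias 1 mm, n = 30 | SD 2 mm | SD 5 mm | SD 10 mm |
|---|---|---|---|
| Rejection rate | 73.9% | 18.2% | 8.5% |
| RMSE (mm) | 2.2 | 5.1 | 10.0 |

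Repeat runs agreed within simulation error. With zero bias, rejection was 4.6% to 5.3% for n from 10 to 50 at all three SDs. The pattern with 1 mm bias was the same at other sizes: 28.3%, 8.9% and 5.7% at n = 10, and 92.6%, 27.6% and 10.3% at n = 50. The typical error rises more than fourfold while the chance of a significant result falls.

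**3. Limits on the proposed summaries.**

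- Order-statistic CI for the median: maximum coverage is 1 − 2 × 0.5ⁿ, which is 93.8% at n = 5 and 96.9% at n = 6. At least 6 patients are needed.
- Distribution-free two-sided CI for the 95th percentile: needs 1 − 0.95ⁿ ≥ 0.975. This is 97.38% at n = 71 and 97.51% at n = 72. At least 72 are needed.
- Exact CI for a proportion, for example 27 of 30: 73.5% to 97.9%.
- Burr hole: assume a circular scalp of radius r = 75 to 100 mm and a hole centre 5 to 8 mm below the scalp. A perfect 30 mm scalp arc then lies (r − depth) × sin(30/r) from midline on CT. This runs from 67 × sin(0.40) = 26.1 mm to 95 × sin(0.30) = 28.1 mm. Geometry alone therefore produces 1.9 to 3.9 mm of apparent deviation from 3 cm.

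**The case against.** The strongest reply is that signed location plus SD is a recognised description of bias and precision, and that direction matters here because the burr hole is deliberately placed to one side. If errors are near normal, the mean and SD give approximate tail shares: with zero bias and SD 5 mm, about 4.6% lie beyond 10 mm. Sets A and B are artificial, with four and two distinct values, and both fail the planned normality test. The raw distances are kept, so absolute errors can be computed at any time. The Wilcoxon simulation shows a property of any location test, against a reference that the plan does not state. The sinus and burr-hole distances add information.

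Much of this stands. The practical loss with ordinary, near-normal data would be smaller than the A/B contrast suggests, and the signed results should be kept. But the sets are not a forecast; they show that the planned summaries do not determine patient-level error. The plan does not take normality for granted, since it tests for it and chooses a nonparametric test. Neither additional distance has a limit, and the sinus distance measures clearance from a different structure. Even where the SD is informative, there is nothing to judge it against.

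**Conclusion.** The concern holds and should be fixed. The reading of the text is certain: distances are signed, and no absolute-error summary, tolerance or success criterion appears anywhere. The practical size cannot be fixed from the document. Under the assumed inputs, the same planned distance summaries are compatible with anything from 10% to 100% of patients beyond 4 mm. The rejection rates further assume normal errors and a reference median of 0. This is a gap in what is reported, not a loss of data: the existing CT measurements can close it.

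**What to change.** - Make the absolute staple-to-midline distance the accuracy measure. Report its mean with a bootstrap 95% CI, its median with an order-statistic 95% CI (if n is at least 6), and the observed 95th percentile and maximum. Give no CI for the 95th percentile unless n is at least 72.
- Report the proportion of patients within a limit in millimetres, with an exact 95% CI. The sponsor should fix the limit before the distances are analysed. The section is written in the past tense; if analysis is already done, label the limit post hoc.
- Keep the signed mean, SD and Wilcoxon test as the bias assessment, and state each reference median. Give mean ± 1.96 SD limits only if normality is acceptable; otherwise give observed percentiles.
- As a secondary summary, report the burr hole's absolute deviation from the planned 3 cm offset. Note that it also includes manual tracing, drilling and scalp-versus-CT geometry, so it is not pure device error. This is the least essential item.
- Keep the distance from sinus as planned.

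The cost is SAP wording and a few lines of code on the same measurements. The headline error will look less favourable because it can no longer average towards zero. Absolute values also lose direction, which is why the signed results stay.

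### Signed distances and a test of difference do not by themselves show localization accuracy: report absolute error and state each theoretical median

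*Combined protocol and SAP*

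**What the plan says.** Under 2. Measurements, the staple-to-midline distance is read from the postoperative CT and carries a sign, with the right side positive: "If the staple was to the left of midline on the postoperative imaging studies, the distance measurement was assigned negative values". The distance from the burr-hole centre to the midline is collected as a "complementary set of measurement data to study the Wishbone's localization accuracy". Distance from sinus and placement time are also recorded; this point does not cover them.

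Under 1. Placement of the Wishbone, the lateral position of the burr hole is set on the scalp: "A second line is manually traced parallel to the midline and 3 cm offset to the right". The text adds: "This second line delineates how far off of the midline the burr hole will be located".

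The Statistical Plan gives the whole analysis in a few sentences. It opens with a distributional check: "Shapiro test was performed to test for normality". The descriptive part then reads: "Mean, median, standard deviation (SD), and 95% confidence interval (CI) values were calculated and reported". The only hypothesis test named for the distances follows: "Wilcoxon signed-rank test (nonparametric) was used to detect statistical difference with theoretical medians". The significance threshold is two-tailed P < 0.05. No theoretical median has a value or is matched to an outcome. There is no limit to set against the CI or SD, and no absolute error or within-limit proportion is planned.

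**The concern.** Localization accuracy asks how far off the device is in individual patients. The planned test asks whether signed distances are centred on a stated value. If that value is the target (0 for the staple, by inference), two things follow.

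- Accuracy sits on the null side. A non-significant result can come from a small sample or from large errors that balance left and right. A significant one can come from a small, consistent shift.
- The mean, median and signed-rank statistic all let opposite errors cancel. Burr-hole errors cancel around their target in the same way.

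At stake is whether the reported results answer the study's own question. A reader given P, mean, median, SD and CI would know the average bias and the scatter. That reader would not know the typical size of a miss, or how many patients were close enough.

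**Working it through.** The plan has no figure to reproduce. It gives no sample size, SD, expected bias or tolerance. The only numerical inputs are two-sided alpha 0.05 and the 3 cm line. Every other n, SD, bias and limit below is assumed for illustration.

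**1. Two constructed data sets, n = 10, null 0, exact signed-rank test (mm).**
- A: -10.5, -9.5, -8.5, -7.5, -6.5, 6, 7, 8, 9, 10. Mean = (40 - 42.5)/10 = -0.25. Mean absolute error = 82.5/10 = 8.25. Positive ranks 1+3+5+7+9 = 25, negative ranks 30. P = 0.85.
- B: 0.5 to 1.4 in steps of 0.1, all to the right. Mean absolute error = 0.95. All signs are equal, so P = 2/2^10 = 0.002.

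The P value favours A, whose errors are almost nine times larger.

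**2. Long-run behaviour (20,000 simulated studies per case, normal errors).**
- Bias 0, SD 10 mm: non-significant in about 95% of studies at every n from 10 to 100, as the test's size requires. Share of patients within 5 mm = 2Φ(5/10) - 1 = 38%; within 3 mm, 24%; within 10 mm, 68%.
- Bias 1 mm, SD 1 mm: significant in 78% of studies at n = 10 and 98% at n = 20, with mean absolute error about 1.2 mm.

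**3. What the planned mean and SD add.** Root-mean-square error = √(bias² + SD²). For the two devices in step 2 this is √(0 + 100) = 10 mm and √(1 + 1) = 1.4 mm, so the planned summaries do separate them. They do not fix the share of patients close to target. Three error distributions with mean 0, SD 5 mm and hence root-mean-square error 5 mm:

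| Errors | Within 5 mm | Median absolute error |
|---|---|---|
| Normal | 68% | 3.4 mm |
| 90% with SD 2 mm, 10% with SD 14.6 mm | 92% | 1.5 mm |
| Clustered at ±4.5 mm, SD 2.18 mm about each | 59% | not computed |

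The planned Shapiro test fails to reject the second case in 59%, 31% and 5% of studies at n = 10, 20 and 50, so it often would not warn a small study.

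**4. Average bias and individual error need separate limits.** Take bias 0.5 SD and a limit of 1 SD.

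| n | Wilcoxon P >= 0.05 | 95% CI of mean (t-based) inside ±1 SD |
|---|---|---|
| 10 | 71% | 28% |
| 20 | 46% | 57% |
| 50 | 8% | 93% |

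The two readings move in opposite directions as n grows. The share of patients within 1 SD is Φ(0.5) - Φ(-1.5) = 0.691 - 0.067 = 62% at any n. A CI inside a limit is therefore no statement about individual patients.

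**5. What a small study can support.** If all n patients are within the limit, the exact 95% lower bound is 0.025^(1/n): 69% at n = 10 and 83% at n = 20.

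**6. Scale of the burr-hole target.** The 3 cm is drawn on the scalp; the outcome is measured on CT. For a spherical head with scalp radius R of 70 to 90 mm and scalp thickness t of 5 to 10 mm (both assumed), (R - t)·sin(30/R) runs from 60·sin(30/70) = 24.9 mm to 85·sin(30/90) = 27.8 mm. This shows only that the scale should be stated; nothing below rests on it.

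**The case against.** The strongest reply is that the plan does not rest on the test. It reports a mean, median, SD and 95% CI; the CI is itself inferential, and mean and SD together give root-mean-square error without assuming normality. This stands. A reader might infer that the Wilcoxon test is the only inference, or that nothing planned measures the size of error. Neither is supported. What is missing is narrower: the typical absolute error and the within-limit share, which step 3 shows cannot be recovered from the SD.

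A second reply is that the medians are easy to guess: 0 for the staple and 3 cm for the burr hole. This largely stands, and writing them down is mainly a matter of completeness. Stating them would not turn a test of difference into evidence of accuracy.

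A third is that the plan never says a non-significant result will be read as accuracy. That is correct. A reader might infer such an intention, but the text says only that the test looks for a difference.

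Finally, the figures above use assumed inputs, and the mixtures in step 3 were chosen to make the point. They show what can happen, not what did happen in this study.

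**Conclusion.** The point holds in this form: signed summaries and a test against unstated medians do not by themselves answer a question about localization accuracy, and the plan lacks a summary of absolute error. It should be fixed because the better summary is almost free. With assumed inputs, the test is non-significant in about 95% of studies for a device that puts only 38% of patients within 5 mm, and significant in 78% (n = 10) to 98% (n = 20) for one with a mean absolute error of about 1.2 mm.

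This rests on reading the staple null as 0, which is an inference. If a theoretical median were instead an error limit, the P value would mean something else, which is a further reason to state it.

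Two stronger conclusions are not supported. The documents do not show that the device is inaccurate or that the investigators misread a P value. Nor does the scalp-versus-CT geometry show that a burr-hole test is invalid: the 3 cm null is inferred, and the head dimensions are assumed. It does not affect the weight of this point.

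**What to change.** 1. Make the absolute staple-to-midline distance the main accuracy summary: median, range and individual values. Report absolute burr-hole error from its target as complementary, noting that it also reflects manual tracing and drilling.
2. Add the proportion of patients within an individual-error limit set by the investigators, with an exact 95% CI. The plan is written in the past tense; if the limit is set after the data were seen, label it post hoc.
3. For each Wilcoxon test, name the outcome and the theoretical median. Say whether the burr-hole target is the 3 cm scalp line or its CT equivalent.
4. Report the 95% CI of the signed mean (or of the median, named as such) as the measure of average bias. If it is to be judged against a margin, set one separately from the individual-error limit. Do not read P >= 0.05 as accuracy.

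Cost: wording, stated targets, an individual-error limit and slightly more reporting, all from CT distances already planned. The downside is that a small study may be unable to support a strong accuracy claim, as step 5 shows, and a post hoc limit supports it less.
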